1.0 HYPOTHESIS AND OBJECTIVES

Hypothesis

Ruxolitinib (also known as INCB018424), a JAK1/2 inhibitor, and lenalidomide (immunomodulatory inhibitory drug; IMiD) are effective and tolerable treatments for patients with myelofibrosis (MF). Combination of these agents in patients with MF can improve the overall clinical response to therapy without causing excessive toxicity.

Objectives

Primary:

- to determine the efficacy of the combination of INCB018424 with lenalidomide in patients with MF, in achieving objective improvements in disease status

Secondary:

- to determine the safety of the combination in patients with MF

Exploratory:

- to explore time to response and duration of response
- to explore the effect of the combination on anemia and transfusion dependence in patients with MF
- to explore changes in JAK2V617F allele burden

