5.0 TREATMENT PLAN

Four weeks on therapy is considered one cycle of therapy. INCB018424 and lenalidamide will be given orally in an outpatient setting. INCB018424 will be given continuously daily in 28-day cycles, and lenalidamide will be given on days 1-21 of 28 day cycles. Dosage for cycles can be reduced, increased or delayed based assessment of efficacy and on adverse events, if any occur, as described below. Delays of a maximum of 8 weeks are allowed from scheduled next cycle.

Subjects will be asked to maintain a diary to record drug administration. Subjects will be asked to bring any unused study drug to the research center at their next visit. Research personnel will count and record the number of used and unused study drug capsules/tablets (both ruxolitinib and lenalidomide) at each visit and reconcile with the subject diary. The study coordinator will question the patient regarding adherence to the dosing regimen, record the number of capsules/tablets and strengths returned in the carton, the date returned and determine treatment compliance before dispensing new medication to the study patient. Compliance below 80% will require counseling of the patient by study site personnel.

The planned dose and schedule of investigation of INCB018424 is 15 mg orally twice daily (BID), continuously in 28-day cycles. Lenalidomide will be taken orally 5 mg/day in the morning each day on days 1-21, followed by 7 days of no therapy of each 28-day cycle; medication will be mailed to participants, per the RevAssist® Program.

Twenty eight days is considered one cycle of therapy. Attempts will be made to provide an adequate treatment period of at least 6 months unless significant toxicity observed, to account for delayed time to response observed with biologic agents. Responders will continue therapy for 6 years unless progression of disease or toxicity warranting discontinuation of therapy is observed.

Prednisone will be added for patients who have not responded after 3 cycles of therapy. It will be dosed orally at the dose of 30 mg/day during cycle 4, 15 mg/day during cycle 5, and 15 mg every other day during cycle 6, and then it will be discontinued.

All patients will be registered in the Clinical Oncology Research system(CORE) at MD Anderson Cancer Center after the informed consent is signed.

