5.6 Evaluation During Study

- Directed history and physical examination including vital signs, body weight, and spleen and liver measurements prior to each cycle for the first 3 cycles then every 3 to 6 cycles. This also includes a transfusion history for previous cycle of therapy and concomitant medication notation.
- CBC and differential, electrolytes (Na, K, Cl HCO₃), creatinine, BUN, glucose, total bilirubin, and SGPT weekly for 2 cycles, then every 2 weeks while on therapy. Those responding patients continuing therapy past 6 cycles and on a stable dose level without interruption or delay for 4 cycles may have blood tests done monthly)
- Bone marrow aspiration with cytogenetics (if abnormal pre-therapy), JAK2V617F allele burden (if JAK2V617F mutation present pre-therapy) after cycle 3,6,9,12 and then as determined appropriate by the investigator.
- Response assessment (IWG-MRT) monthly for first 3 cycles, then every 3 to 6 cycles
- Pregnancy test, urine or blood, (sensitivity of at least 50 mIU/mL) every week x 4, then every 4 weeks for all FCBP with regular menstrual cycles, or every 2 weeks if irregular cycles.
- Optional blood samples (20-50cc) on day 1 of cycle 2 for pharmacokinetics (PK) at approximately 0.5-1 hour, 2-4 hours, and 4-8 hours post ruxolitinib dose (3 time points). Not all research samples may be collected at all time points.
- Collect any unused study drug and review patient study drug dosing diary for compliance;
- Assessment of AEs using the NCI CTEP CTCAE, version 4.0 (published 28 May 2009)
- Myelofibrosis Symptom Assessment Form (MFSAF) questionnaire every cycle x3, then every 3 to 6 cycles
- MDASI (MD Anderson Symptom Inventory) questionnaire administration: patients will complete the paper or tablet PC version of the MDASI at every cycle x3, then every 3 to 6 cycles. Patients will be instructed in the use of an Interactive Voice Response (IVR) system that will be used to assess symptoms with the MDASI weekly for first 3 cycles of therapy when patients do not have clinic appointments. If patients do not respond to an IVR call, the research coordinator will attempt to personally contact the patient by telephone to complete the MDASI.

Outside Physician Participation During Treatment

- MDACC Physician communication with the outside physician is required prior to the patient returning to the local physician.
This will be documented in the patient record

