- An increase in peripheral blood blast percentage of $\geq 20\%$ that lasts for ≥ 8 weeks.

Stable disease: None of the above.

Relapse: Loss CR, PR, and CI. In other words, a patient with CR or PR is considered to have undergone relapse when he or she no longer fulfills the criteria for CI.

**Because of subjectivity in peripheral blood smear interpretation, CR does not require absence of morphological abnormalities of red cells, platelets, and neutrophils.*

*** In patients with CR, a complete cytogenetic response is defined as failure to detect a cytogenetic abnormality in cases with a pre-existing abnormality. A partial cytogenetic response is defined as 50% or greater reduction in abnormal metaphases. In both cases, at least 20 bone marrow- or peripheral blood-derived metaphases should be analyzed. A major molecular response is defined as the absence of a specific disease-associated mutation in peripheral blood granulocytes of previously positive cases. In the absence of a cytogenetic/molecular marker, monitoring for treatment-induced inhibition of endogenous myeloid colony formation is encouraged. §Transfusion dependency is defined by a history of at least 2 units of red blood cell transfusions in the last month for hemoglobin of < 8.5 g/dL that was not associated with clinically overt bleeding. Similarly, during protocol therapy, transfusions for hemoglobin of ≥ 8.5 g/dL is discouraged unless it is clinically indicated.*

§§In splenectomized patients, palpable hepatomegaly is substituted with the same measurements.

¶It is acknowledged that worsening cytopenia might represent progressive disease but its inclusion as a formal criterion was avoided because of the difficulty distinguishing disease-associated from drug-induced myelosuppression. However, a decrease in hemoglobin of ≥ 2 g/dL, a 100% increase in transfusion requirement, and new development of transfusion dependency, each lasting for more than 3 months after the discontinuation of protocol therapy can be considered disease progression.

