The severity of the toxicities will be graded according to the NCI CTCAE v4.0 whenever possible. We will follow standard reporting guidelines for adverse events (Appendix C; Leukemia-specific Adverse Event Recording and Reporting Guidelines).

Descriptive statistics will be utilized to assess time to response and response duration.

Duration of response: duration of response is defined as the date at which the subject's objective status is first noted to be a CR, PR or CI to the date progression (no longer meeting criteria for either CR, PR or CI) is documented (if one has occurred). Patients who continue to respond as of the data cut-off date will be censored as of the date of their last assessment documenting continued response.

Time to response: The time to response is defined as the time from study registration to the first date at which the subject's objective status was classified as a response (CR, PR or CI). In subjects who do not achieve a response, time to response will be censored at the subject's last evaluation date. The distribution for each of these event-time variables (duration of response and time to response) will be estimated by Kaplan-Meier curves.

Anemia: Descriptive statistics will be used to explore improvements in anemia and transfusion dependence. The following outcomes will be summarized: mean changes in hemoglobin at monthly intervals. The proportion of transfusion independent patients not requiring transfusions on study who experience an increase of 2 g/dL in their hemoglobin relative to baseline, the proportion of transfusion dependent patients (defined as requiring a transfusion of 2 units PRBCs monthly for 3 months (12 weeks) prior to starting the trial) who become transfusion independent (not requiring a transfusion of PRBCs over a period of 3 months (12 weeks) while on study), the proportion of transfusion dependent patients who become transfusion independent and have a 1 g/dL increase in hemoglobin relative to baseline, and the proportion of transfusion independent patients requiring a transfusion while on study.

JAK2V617F Allele burden: Change in JAK2V617 allele burden from baseline to each visit where it is measured.

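### Death is not an event for duration of response, so deaths in response are censored by default and time alive and in response is overstated

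*Combined protocol and SAP*

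**What the plan says.** Section 1.0 places this endpoint among the exploratory objectives: "to explore time to response and duration of response". Section 8.0 starts the clock when CR, PR or CI is first noted and runs it "to the date progression (no longer meeting criteria for either CR, PR or CI) is documented (if one has occurred". It gives one censoring rule: "Patients who continue to respond as of the data cut-off date will be censored as of the date of their last assessment" that shows continuing response. The estimator is Kaplan-Meier: "duration of response and time to response) will be estimated by Kaplan-Meier curves".

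No other section gives death a role in this endpoint. Section 6.0 defines relapse through the response criteria alone: "a patient with CR or PR is considered to have undergone relapse when he or she no longer fulfills the criteria for CI". Its progression criteria cover spleen growth, leukemic transformation and rising blasts. Section 5.7 lists death only as a reason to stop study treatment.

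Two design features bear on the point. Section 5.0 allows long treatment: "Responders will continue therapy for 6 years unless progression of disease or toxicity warranting discontinuation of therapy is observed". Section 5.6 schedules response assessment "monthly for first 3 cycles, then every 3 to 6 cycles", and Appendix I gives the later interval as 84 to 168 days.

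**The concern.** A patient who dies in response never has loss of response documented, so the definition yields no event date. Kaplan-Meier allows only an event or a censored time, so that patient is censored. Censoring treats the patient as someone who could still have lost response later, at the same rate as those still under observation. At best, the curve then describes how long response would last if nobody died. A reader who takes it as the time patients spend alive and in response is given too long a duration.

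The visit spacing adds a second problem. A patient who deteriorates and dies between two assessments 84 to 168 days apart may have no documented loss, and would be censored at the last good assessment. Interim blood counts or local visits may catch some of these losses, but the spleen measurement and the formal response assessment are not due in between. Such censoring is related to the outcome, so the curve can be too high even as an estimate of time to loss of response.

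Durability is a named objective, and the protocol itself cites response durations from earlier studies as evidence (Sections 2.2 and 2.3). The figure from this trial is likely to be read in the same way.

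**Working it through.** The documents state no figure for duration of response, so there is none to reproduce. The size can only be illustrated.

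**Inputs**
- M = 18 months, median time to loss of response. This is an assumption, borrowed from the median durability of clinical improvement with lenalidomide plus prednisone (Section 2.3).
- S = 95, 48 and 27 months, median survival for intermediate-1, intermediate-2 and high risk (Appendix II). These are the risk groups eligible if newly diagnosed (Section 4.0).
- f = death hazard while in response, as a share of the risk-group hazard. The documents give no value; the assumed range is 0.25 to 1.
- Times to loss of response and to death are independent and exponential (assumption).

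**Formulas**
- Hazard of loss of response: ln2/M. Hazard of death in response: f × ln2/S.
- Median with deaths censored: M = 18.
- Median with death as an event: 1/(1/M + f/S) = M × S/(S + f × M).
- Overstatement: M divided by that median, minus 1, which equals f × M/S.
- Share of responses that end in death: f × M/(S + f × M).

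**Results**

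| Risk group | Median, f = 0.25 | Median, f = 1 | Overstatement | Responses ending in death |
|---|---|---|---|---|
| Intermediate-1 (S = 95) | 1710/99.5 = 17.2 | 1710/113 = 15.1 | 5% to 19% | 4.5% to 15.9% |
| Intermediate-2 (S = 48) | 864/52.5 = 16.5 | 864/66 = 13.1 | 9% to 38% | 8.6% to 27.3% |
| High (S = 27) | 486/31.5 = 15.4 | 486/45 = 10.8 | 17% to 67% | 14.3% to 40.0% |

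The proportion in response at 12 months is 2^(−12/18) = 63% with deaths censored. Putting the medians above in place of 18 gives 62%, 60% and 58% at f = 0.25, and 58%, 53% and 46% at f = 1 (intermediate-1, intermediate-2, high). With f = 0 the two definitions agree.

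**Primary decision.** The two-stage rule counts responders (10 of 31, then 21 of 49) and does not use duration. Exact binomial sums reproduce its stated properties: early termination 0.455 at a 35% response rate (stated 46%), type I error 0.097 (limit 10%) and power 0.801 at 50% (stated 80%).

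**The case against.** A reader might infer that the plan instructs the analyst to censor deaths. It does not. The one written rule is for those still responding at data cut-off, and a patient who died earlier is not among them. Death could, with strain, be read as no longer meeting the response criteria, although the event must be documented as progression. So the censoring is a default that follows from the event definition and the estimator. This corrects the wording but leaves the problem: death is not a listed event, and two analysts could report different medians from the same data.

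A reader might also infer that deaths in response will be common. The documents do not show this. Appendix II gives overall survival for whole risk groups, including deaths after response is lost. Section 2.1 attributes death to marrow failure, leukemic transformation and portal hypertension. Leukemic transformation is progressive disease under Section 6.0, so some of these deaths would follow an event already counted. This is a good reason to expect f below 1 and to show the whole range.

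The 6 years in Section 5.0 might be taken as follow-up, but it is a treatment limit. After discontinuation, the contacts specified are at 30 and 60 days, for adverse events (Section 5.6, Appendix I). Later deaths may not be captured.

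The shift may also be small beside sampling error. With about 24 responders (50% of 49), all with events, an approximate 95% interval for an 18-month median is 18 × exp(±1.96/√24), or 12 to 27 months. At f = 0.25 the shift is only 18 − 17.2 = 0.8 to 18 − 15.4 = 2.6 months. That is fair as to scale, but the shift is systematic and always lengthens the reported duration.

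Finally, overstatement is relative to time alive and in response. An analyst who wants time to loss of response has another valid course, the cumulative incidence of loss with death as a competing event. The plan provides for neither.

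**Conclusion.** The point holds, with limited consequence. As defined, duration of response has no event for a patient who dies in response. Kaplan-Meier then censors that patient by default, and the result overstates time alive and in response.

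Under the assumptions shown, the overstatement of the median runs from about 5% (intermediate-1, f = 0.25) to 67% (high risk, f = 1). The upper end should not be taken as the expected effect: 10.8 months requires every responder to be high risk and to die at the full risk-group rate. The 18-month input comes from another regimen, where nine patients had clinical improvement. The documents cannot fix the true size, and it is zero if nobody dies in response.

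The endpoint is exploratory and descriptive. Nothing here supports doubt about the response-rate decision. The rule should still be settled before analysis.

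**What to change.** In the duration-of-response paragraph of Section 8.0, define the end of response as the earlier of documented loss of CR/PR/CI and death from any cause. State that patients who withdraw or are lost while responding are censored at their last assessment documenting response. If time to loss of response is also wanted, report its cumulative incidence with death as a competing event.

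The cost is a sentence or two, with no change to sample size, visits or the two-stage rule. The downside is that the reported duration becomes shorter, by an amount that depends on how many patients die in response.

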APPENDIX I: SCHEDULE OF ASSESSMENTS

Procedure	Screening Period ≤14 days from Day 1 (first day of study drug administration)	Cycle 1 ⁹ and 2				Cycle 3 ⁹ Every 28 days	After Cycle 3 or at discontinuation ⁹ Every 3 to 6 Cycles (84 to 168 days)
		Day 1 ⁵	Day 8	Day 15	Day 22		
Informed Consent signing	X						
Medical History (including prior MF-directed therapies)	X						
Physical examination ¹	X	X		X		X	X
Vital Signs and Weight, Height ¹¹	X	X		X		X	X
Transfusion History ²	X ²					X	X
MFSAF and MDASI questionnaires		X				X	X
Pregnancy test (for FCBP only) ³	X	X	X	X	X	X	X
CBC and differential ⁶	X	X	X	X	X	X ⁶	X ⁶
Serum Chemistry ⁴	X	X	X	X	X	X ⁶	X ⁶
12-Lead ECG and urinalysis	X						
Bone Marrow Aspirate and Biopsy ⁷	X						X ⁸
Correlative studies for PK: Peripheral blood sample x3	-	X ¹⁰					
Assess and Record adverse events	X	X		X		X	X
Record concomitant therapies/procedures	X	X		-		X	X
Response Assessment					X	X	X

¹ Includes measurement of spleen and liver.

² Subjects must have 3 months documented transfusion history prior to Day 1.

³ Pregnancy test, urine or blood, with a sensitivity of at least 50 mIU/mL, within 10 – 14 days prior to and again within 24 hours of starting lenalidomide; then every week x 4, then monthly for all FCBP with regular menstrual cycles, or every 2 weeks if irregular cycles.

⁴ sodium, potassium, chloride, carbon dioxide, blood urea nitrogen, creatinine, total bilirubin, alanine aminotransferase, and glucose. Uric Acid, PT/PTT and INR need be done only pre-therapy.

⁵ If not done within 3 days of Day 1.

⁶ CBC with differential and serum chemistries will be done weekly for 2 cycles, then every 2 weeks while on therapy. Those responding patients continuing therapy past 6 cycles and on a stable dose level without interruption or delay for 4 cycles may have blood tests done monthly.

⁷ Bone Marrow Aspirate and Biopsy (can be done within 3 months) includes standard cytogenetic analysis and JAK2 mutation testing (quantitative PCR for allele burden). Cytogenetic test and JAK2 mutation test do not need to be repeated during the study in patients with known normal chromosomes or without mutation. BM collected after Cycle 3,6,9,12 and then as determined appropriate by the investigator.

⁸ May be omitted if so decided by the treating physician. Should be done to confirm complete response and when clinically indicated.

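### Loss of response is dated at the visit that documents it, after assessments thin to every 12 to 24 weeks, so Kaplan-Meier duration runs some weeks long for early responders

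*Combined protocol and SAP*

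**What the plan says.** Section 5.6 sets the schedule: "Response assessment (IWG-MRT) monthly for first 3 cycles, then every 3 to 6 cycles". Spleen size follows the same pattern: "spleen and liver measurements prior to each cycle for the first 3 cycles then every 3 to 6 cycles". Appendix I heads the later column "Every 3 to 6 Cycles (84 to 168 days"), which agrees with the 28-day cycle in Section 5.0.

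Section 8.0 starts duration of response at "the date at which the subject's objective status is first noted to be a CR, PR or CI" and runs it "to the date progression (no longer meeting criteria for either CR, PR or CI) is documented (if one has occurred"). Patients still in response "will be censored as of the date of their last assessment documenting continued response". For the estimator: "The distribution for each of these event-time variables (duration of response and time to response) will be estimated by Kaplan-Meier curves".

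Section 8.0 gives no rule for a loss that occurs between assessments, no interval-censored method and no sensitivity analysis for visit spacing. The 3-to-6-cycle range is left open. Section 1.0 lists duration of response as exploratory, and Section 8.0 treats it descriptively.

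**The concern.** The two ends of an early response are read on grids of different fineness. Onset in cycles 1 to 3 is located to within about 4 weeks. Its loss usually falls after week 12, where the gap is 12 to 24 weeks. Section 6.0 makes this more likely: a clinical improvement counts only if it lasts at least 8 weeks, so one first noted at week 4 must persist to about week 12. The delay in dating loss is then larger than the delay in dating onset, and the difference enters the recorded duration as if it were time in response.

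At stake is the reported duration curve and median. They could look several weeks better through scheduling alone, by an amount that depends on the spacing used for each patient. The grid also coarsens at the point where Section 5.0 adds prednisone for patients who have not responded after three cycles. An informal comparison of early with late responders would therefore mix this artefact with a difference in treatment. The plan specifies no such comparison.

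**Working it through.** **The plan's own figures.** The documents give no precision target for duration, so there is none to reproduce. The primary design does reproduce. With 10/31 and 21/49, exact binomial sums of P(X1 = x) × P(X2 ≥ 22 − x) over x ≥ 11 give a type I error of 0.0966 at 35% and power of 0.801 at 50%. P(X1 ≤ 10) at 35% is 0.455 (stated: 46%). The rule counts responders and does not use duration.

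**Inputs from the documents.** Cycle of 28 days; assessments at about weeks 4, 8 and 12, then every 84/7 = 12 to 168/7 = 24 weeks; start at first-noted response; end at documented loss; 8-week minimum for clinical improvement.

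**Closed form.** An event that falls at random in a gap of length g is dated g/2 late on average.

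- Early onset: 4/2 = 2 weeks late.
- Loss after week 12: 12/2 = 6 to 24/2 = 12 weeks late.
- Net error against true onset-to-loss: 6 − 2 = 4 to 12 − 2 = 10 weeks.
- Net error against first-noted response to true loss: 6 to 12 weeks.

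**Simulation** (400,000 responders per setting). Assumptions: onset uniform over weeks 0-12 (early) or 12-36 (late); true duration 8 weeks plus an exponential time, with median 26, 52 or 78 weeks; both events seen only at the next scheduled assessment; cut-off at week 156 for the Kaplan-Meier median. The 78-week value matches the 18-month median in Section 2.3 for lenalidomide plus prednisone (18 × 52/12 = 78). Entries are in weeks, for assumed medians 26 / 52 / 78.

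| Spacing | Early: recorded − true onset-to-loss | Early: recorded − (first noted to loss) | Early: Kaplan-Meier median | Late: recorded − true onset-to-loss |
|---|---|---|---|---|
| 12 | +4.0 / +4.0 / +4.0 | +6.0 / +6.0 / +6.0 | 32 / 56 / 84 | +0.2 / +0.1 / +0.1 |
| 18 | +7.2 / +7.1 / +7.1 | +9.2 / +9.1 / +9.1 | 36 / 58 / 90 | −0.2 / −0.9 / −1.2 |
| 24 | +10.6 / +10.3 / +10.2 | +12.6 / +12.3 / +12.2 | 32 / 56 / 96 | +2.6 / +1.1 / +0.7 |

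The mean error hardly depends on the assumed duration. The median moves in visit-sized steps, so its error is uneven: from 52 to 56 at both 12- and 24-week spacing, but from 78 to 84 or 96. The overstatement is an average: 17% (12-week) to 8% (24-week) of early responders have a recorded duration shorter than the true one.

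**Early against late.** At 12-week spacing the difference in mean error is 4.0 − 0.2 = 3.8 to 4.0 − 0.1 = 3.9 weeks. At 24-week spacing it is 10.6 − 2.6 = 8.0 to 10.2 − 0.7 = 9.5 weeks. Overall it is about 4 to 10 weeks.

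**Effect of midpoint dating.** Placing loss midway between the last assessment in response and the first without it cuts the early responders' error from first-noted response. It falls from 6.0 to 0.0-0.1 weeks (12-week spacing) and from 12.2-12.6 to 0.2-0.9 weeks (24-week spacing).

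**The case against.** The strongest objection is that loss need not wait for a scheduled response visit. Section 5.6 has blood counts every 2 weeks (monthly for some stable responders), which can show loss of a hemoglobin, platelet or neutrophil improvement. The Appendix I notes require visits at least every 28 days, locally if need be. Its last column also covers discontinuation, with response assessment and physical examination. Section 8.0 says only that loss is documented, not where. This stands, and it makes 4 to 10 weeks an upper range. If half of losses were caught at 4-weekly contacts (an assumption), their loss lag of 2 weeks would cancel the onset lag. The mean error would fall to 0.5 × 4 = 2 or 0.5 × 10 = 5 weeks. It does not remove the point for spleen responses, because spleen measurement is not scheduled at those interim contacts and Section 8.0 does not say whether such dates count.

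The consequence is also modest. At 35% to 50% response, 49 patients give about 17 to 25 responders. For an exponential 78-week median without censoring, the standard error of the sample median is about 78/(0.693 × √n), or 27 weeks at n = 17 and 23 at n = 25. That exceeds the bias. This stands too, though a bias of known direction does not average out as sampling error does.

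It can also be said that first-noted response to documented loss is a defined quantity, which Kaplan-Meier estimates correctly. That is fair, but readers will take it as time in response.

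Three stronger readings are tempting and not supported:

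- **An early/late gap of 16 weeks.** This needs all late onsets in weeks 12-24 of a gap that runs to week 36. Onset is then dated 18 weeks late on average, the net late error is 12 − 18 = −6, and 10 − (−6) = 16. Nothing in the documents confines onset to that half of the gap.
- **Bias between clinics.** Patients return to one centre for evaluation. Spacing may vary between patients, but no clinic-by-clinic response schedule is described.
- **A median one third too long.** A shift from 36 to 48 weeks needs a short assumed duration and the loosest spacing for every patient. The only median duration in the documents is 18 months.

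**Conclusion.** The concern holds as a minor but directional weakness in an exploratory analysis. For responses that begin in cycles 1 to 3 and whose loss is seen only at scheduled response visits, mean recorded duration is too long. The excess is about 4 weeks (12-week spacing) to 10 weeks (24-week spacing) against true onset-to-loss, and about 6 to 12 weeks against first-noted response. Off-schedule documentation of loss would reduce both. Later responders show little net error in onset-to-loss (−1.2 to +2.6 weeks), because both ends are then read on the coarse grid.

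The result rests on a regular visit grid, no drift within the 7-day window, and onset spread evenly over the stated periods. The 10/31 and 21/49 decision, the sample size and the error rates are untouched.

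**What to change.** In Section 8.0:

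1. Keep the start as the date response is first noted.
2. Record loss as the interval from the last assessment in response to the first assessment not in response. The censoring rule already needs the first of these dates.
3. Estimate duration with an interval-censored (Turnbull) estimator. At minimum, report a midpoint-dated analysis beside the Kaplan-Meier curve.
4. State that an off-schedule count or examination that shows loss sets the end of the interval.
5. Report the assessment spacing actually used.

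Making only the loss an interval keeps this a standard problem. Intervals at both ends would be doubly interval-censored, which the ordinary Turnbull estimator does not handle.

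The cost is a little analysis work and, in all likelihood, a reported median some weeks shorter. No new data or visits are needed. Two limits should be stated with the result. First, midpoint dating corrects the mean but not the stepping of the median. At 24-week spacing the midpoint medians were 20, 44 and 84 weeks, against 24, 50 and 76 from first-noted response. Second, a first-noted start is itself late for late responders, by about 6 weeks (6.0 − 0.1 = 5.9) at 12-week spacing and 12 weeks (12.4 − 0.7 = 11.7) at 24-week spacing, against 2 weeks for early responders. The result should therefore be labelled as duration from first-noted response and not used to compare early with late responders.
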